2.5.6.2 Exploratory endpoints

2.5.6.3 PCSK9 targeting non-study medication or lipid apheresis supplementary analysis

With a supplementary analysis the impact of allowing the use of PCSK9 targeting non-study medication or lipid apheresis will be investigated. Therefore, the individual LDL-C target of participants receiving PCSK9 targeting non-study medication or lipid apheresis will not be

considered a treatment failure (composite strategy). For this supplementary strategy the primary analysis will be repeated but LDL-C values observed during or after the use of a PCSK9 targeting non-study medication or lipid apheresis will be evaluated according to participant-individual LDL-C target as measured.

2.6 Analysis supporting secondary objectives

2.6.1 Secondary endpoint(s)

The population and the treatment of interest associated with the secondary estimand are the same as for the primary estimand (see [Section 1.2.1](#)).

The secondary estimands are defined by the evaluation of treatment effect on the following endpoints and summary measures in [Table 2-3](#):

Table 2-3 Endpoints and summary measures of the secondary estimand

Endpoint	Summary Measure
Relative change (percentage change) from baseline to mean LDL-C level over the double-blind study period (averaged over all post baseline visits)	Difference in mean relative change
Proportion of participants experiencing at least one muscle-related AE as defined in the SMQ rhabdomyolysis / myopathy from Day 1 to Day 360	OR (odds ratio)
Annualized number of days participants experiencing self-reported pain from Day 1 to Day 360	Annualized RR (rate ratio)
Change from baseline in SF-BPI pain severity score at Day 360	Difference in mean relative change
Change from baseline in SF-BPI pain interference score at Day 360	Difference in mean relative change
Proportion of participants with clinically relevant change in SF-BPI pain severity score from baseline to Day 360.	OR (odds ratio)
Proportion of participants with clinically relevant change in SF-BPI pain interference score from Baseline to Day 360.	OR (odds ratio)

2.6.2 Statistical hypothesis, model, and method of analysis

For muscle-related AE / SMQ rhabdomyolysis / myopathy the SAF will be used for analysis. For all other secondary efficacy analyses the FAS will be used.

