12.1 Analysis sets

The **screened set (SCR)** consists of all participants who signed the informed consent. The SCR includes only unique screened participants, i.e., in the case of re-screened participants only the chronologically last screening data is counted.

The **run-in set (RIS)** consists of all patients who enter the run-in phase.

The **randomized set (RAN)** consists of all participants who received a randomization number, regardless of receiving trial medication.

The **full analysis set (FAS)** consists of all randomized participants who received at least one dose of double-blind study medication. Following the intent-to-treat principle, participants will be analyzed according to the treatment to which they were assigned at randomization. Efficacy variables will be analyzed based on the FAS.

The **safety set (SAF)** includes all participants who received at least one dose of study treatment. Participants will be analyzed according to the study treatment received. The SAF will be used for the analyses of safety and tolerability variables.

The **AP set** is a subset of the FAS and includes participants with a diagnosis of angina pectoris at baseline.

The **PAD set** is a subset of the FAS and includes participants with a diagnosis of peripheral artery disease at baseline.

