2.2 Analysis sets

The **screened set (SCR)** consists of all participants who signed the informed consent. The SCR includes only unique screened participants, i.e., in the case of re-screened participants only the chronologically last screening data is counted.

The **run-in set (RIS)** consists of all participants who enter the run-in phase.

The **randomized set (RAN)** consists of all participants who received a randomization number, regardless of receiving trial medication.

The **full analysis set (FAS)** consists of all randomized participants who received at least one dose of blinded investigational treatment. Following the intent-to-treat principle, participants will be analyzed according to the treatment to which they were assigned at randomization. Efficacy variables will be analyzed based on the FAS.

The **safety set (SAF)** includes all participants who received at least one dose of blinded investigational treatment. Participants will be analyzed according to the blinded investigational treatment received. A participant who receives any amount of double-blind inclisiran throughout the study will be analyzed within the inclisiran treatment group for the safety analyses. Concomitant use of commercially available inclisiran during the study will

not be considered, those are considered as part of the intercurrent events. The SAF will be used for the analyses of safety and tolerability variables.

Additionally, the **AP set** is a subset of the FAS and includes participants with a diagnosis of angina pectoris at baseline, i.e. participant has a recorded medical history of stable angina or unstable angina. and the **PAD set** is a subset of the FAS and includes participants with a diagnosis of peripheral artery disease at baseline, i.e. participant has a recorded medical history of peripheral artery disease.

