2.6.2.2 Proportion of muscle-related adverse events

The null hypothesis to be rejected for the relevant secondary endpoint is:

- H_{03} : The odds regarding participants experiencing at least one muscle-related AE as defined in the SMQ rhabdomyolysis / myopathy from Day 1 to Day 360 are equal between treatment groups.

Muscle-related AEs are defined by the SMQ rhabdomyolysis / myopathy (covering narrow and broad search). The proportion of participants experiencing at least one muscle-related AE from Day 1 to Day 360, i.e. occurring between first dose of double-blind treatment up to the minimum of last contact date and Day 360 visit date, will be analyzed in a logistic regression model. Treatment and CV risk category will be included as factors in the model. The odds ratio and its 95% confidence interval (CI) and p-value will be estimated.

Additionally, the relative risk as well as absolute risk difference and their 95% confidence intervals will be estimated from a Cochran-Mantel-Haenszel test (CMH) stratified for CV risk category.

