2.7 Safety analyses

All safety parameters will be analyzed based on the SAF, including the secondary safety endpoint.

All listings and tables will be presented by treatment group. Safety summaries (tables, figures) include all data from the double-blind treatment period (i.e. post-baseline assessments) and baseline data.

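### The confirmatory muscle-AE test (H03) groups participants by treatment received, which is not aligned with the randomized comparison in the estimand it inherits: a minor point, cheap to fix

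*SAP*

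**What the plan says.** H03 states equal odds of at least one muscle-related AE in the two arms. SAP 2.6.2.5 and Protocol 12.5.1 place it with H02 in the second family of the alpha-controlled hierarchy. The third family (H04 to H06) is tested only if both H02 and H03 are rejected.

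For this endpoint SAP 2.6.2 says "For muscle-related AE / SMQ rhabdomyolysis / myopathy the SAF will be used for analysis", and Protocol 12.5.2 makes the same assignment. Every other secondary efficacy analysis uses the FAS. On grouping, SAP 2.2 says of the SAF: "Participants will be analyzed according to the blinded investigational treatment received". It adds: "A participant who receives any amount of double-blind inclisiran throughout the study will be analyzed within the inclisiran treatment group for the safety analyses". SAP 2.7 brings H03 under that rule: "All safety parameters will be analyzed based on the SAF, including the secondary safety endpoint". For the FAS, by contrast, SAP 2.2 says: "Following the intent-to-treat principle, participants will be analyzed according to the treatment to which they were assigned at randomization".

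The protocol's SAF definition (12.1) is as-treated too, "Participants will be analyzed according to the study treatment received", but has no rule for mixed exposure. That rule appears only in the SAP and is not among the changes listed in SAP section 4.

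SAP 2.6.2.2 counts events "occurring between first dose of double-blind treatment up to the minimum of last contact date and Day 360 visit date", with no split at the date of a wrong injection. On the estimand, SAP 2.6.1 says: "The population and the treatment of interest associated with the secondary estimand are the same as for the primary estimand". The primary estimand (SAP 1.2.1) names the compared treatments as the randomized ones.

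**The concern.** In a descriptive AE table, as-treated grouping is conventional. H03 is a claim that one randomized strategy causes fewer events than the other, and for that claim a post-randomization event should not redefine the arms.

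The rule also treats the arms differently when exposure is mixed. A placebo participant given one inclisiran syringe moves to inclisiran. An inclisiran participant given one placebo syringe stays where they are. Only a participant randomized to inclisiran who received nothing but placebo would move the other way. For a placebo participant who moves, events that occurred before any inclisiran exposure are charged to inclisiran.

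At stake are the interpretation of H03 as a randomized comparison and, in a borderline case, whether the third family is opened. No as-randomized analysis of H03 is planned that would show whether the grouping mattered.

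**Working it through.** **The plan's own figure.** SAP 3.2 gives 90% power for a condition on the risk-ratio confidence interval. The rates, threshold and sample size are redacted, so it cannot be reproduced. Nothing below depends on it.

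**Time before exposure.** The injection days are 1, 90 and 270 (SAP 2.1.1.1). For a first inclisiran injection given in error at Day 270, the share of the window before exposure is 269/360 = 75%. At Day 90 it is 89/360 = 25%.

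**Shift in the odds ratio.** Inputs: 1776 randomized (Protocol, Amendment 3 rationale), taken as 1776/2 = 888 per arm. The event rates p0 (placebo) and p1 (inclisiran) and the number k of placebo participants moved are assumptions. Those moved carry the placebo rate.

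- Rate in the inclisiran column: q = (888·p1 + k·p0)/(888 + k)
- OR = [q/(1 − q)] / [p0/(1 − p0)]
- Example, 10% vs 7%, k = 10: q = (62.16 + 1.00)/898 = 0.07033; OR = 0.07566/0.11111 = 0.681

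| Assumed rates (placebo vs inclisiran) | k = 0 | k = 5 | k = 10 | k = 20 |
|---|---|---|---|---|
| 10% vs 7% | 0.677 | 0.679 | 0.681 | 0.684 |
| 15% vs 10.5% | 0.665 | 0.667 | 0.668 | 0.672 |

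**Power.** Pooled-variance two-proportion z-test, planned 880 per arm, assumed 10% vs 6%. H03 is tested at one-sided 0.025, or at 0.2 × 0.025 = 0.005 when the two p-values in the family are not both at or below 0.025.

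| Placebo participants moved | OR | Power at 0.025 | Power at 0.005 |
|---|---|---|---|
| 0 | 0.574 | 87.2% | 69.8% |
| 9 (1%) | 0.579 | 86.5% | 68.6% |
| 44 (5%) | 0.594 | 83.5% | 64.2% |

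**Type I error.** Null simulation with 200,000 replicates, 880 per arm, 10% event rate in both randomized arms, nominal one-sided 0.025. Columns give the AE risk of mis-dosed placebo participants relative to the placebo arm's 10% rate.

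| Placebo mis-dosed | Half the risk | Same risk | Twice the risk |
|---|---|---|---|
| 1% | 0.030 | 0.025 | 0.017 |
| 5% | 0.054 | 0.025 | 0.004 |

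**A borderline result.** Take 62 vs 88 events in 880 per arm. The pooled rate is 150/1760 = 0.0852, the standard error is 0.0133 and the difference is 26/880 = 0.0295, so z = 2.22 and one-sided p = 0.013. Moving one placebo participant with an event gives p = 0.020. Moving three, all with events, gives p = 0.040, which crosses 0.025. At a 10% event rate, the chance that three participants chosen without regard to outcome all have events is 0.1³ = 0.001.

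**The case against.** The SAF choice is deliberate. Both documents treat this as a safety endpoint, assign it to the SAF and contrast it with the FAS endpoints. The mixed-exposure rule also suits a long-acting drug, for which SAP 2.4.1 attributes 180 days of exposure to each injection. No document reports any mis-dosing. Syringes are assigned through IRT by medication number and injected at site by qualified staff (Protocol 6.3, 6.3.2), so errors should be rare. All of this stands. It limits the size of the problem, but it does not explain why a confirmatory superiority test should be grouped by treatment received.

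A reader might infer stronger things that the documents do not support:

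- That the analysis contradicts the treatment-policy strategy. SAP 2.6.3 applies that strategy to treatment discontinuation, PCSK9-targeting medication or apheresis, and COVID-19. A wrong syringe is none of these. The wording about arms as assigned stands in the primary-estimand rules (SAP 2.5.3). The mismatch is with the randomized-treatment comparison that H03 inherits. Commercial inclisiran is also outside the rule, because SAP 2.2 treats it as part of the intercurrent events.
- That the rule favours inclisiran. Errors unrelated to outcome pull the odds ratio toward 1 and leave type I error at 0.025. Inflation needs mis-dosed placebo participants to have lower AE risk, and nothing in the documents suggests that.
- That the FAS and SAF always hold the same people. SAP 2.2 and Table 5-5 require randomization for the FAS but only a blinded dose for the SAF. The sets match for randomized participants; someone dosed without randomization could be in the SAF alone.
- That errors clustered by site would make the effect large. In the odds-ratio calculation only the number moved and their event rate matter, and clustering was not modelled.

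**Conclusion.** The point holds as one of alignment. H03 is a confirmatory gatekeeping test whose estimand compares randomized treatments, while its analysis lets treatment received decide the group. The severity is minor. If nobody was mis-dosed, the two analyses give the same result for randomized participants. If a few errors occurred independently of outcome, the change is in the third decimal of the odds ratio and is conservative. The example in which the test crosses 0.025 is an adverse scenario, not an expectation. All event rates, mis-dosing counts and relative risks used here are assumptions, because the plan's rates are redacted and no mis-dosing count is given.

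**What to change.** In SAP 2.6.2.2 and 2.6.5, run the H03 logistic regression, the Mantel-Haenszel risk ratio and risk difference, and the Cox sensitivity analysis on the FAS by randomized arm. Keep the as-treated SAF version of H03 as a supportive analysis, and keep the SAF for the descriptive AE tables. Align the sentence in SAP 2.6.2, and record the change in SAP section 4 or amend Protocol 12.5.2. This should be settled before unblinding.

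The cost is a changed grouping variable, a documented departure from the protocol-specified analysis set and one extra supportive analysis. No new data are needed.

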2.6.2.1 Mean relative change in LDL-C

The null hypothesis to be rejected for the relevant secondary endpoint is:

- H_{02} : The mean relative changes from baseline in LDL-C level, averaged over all post baseline visits during the double-blind treatment period, are equal between treatment groups.

The relative change (percentage change) from baseline in LDL-C level averaged over the double-blind treatment period will be analyzed using a mixed model for repeated measures (MMRM) including treatment group, CV risk category, scheduled visit and the interaction of treatment group with scheduled visit as factors and baseline LDL-C level and the interaction of baseline LDL-C level with scheduled visit as covariates. To allow adjustment for correlations between time points within participants, an unstructured variance-covariance structure will be used. The null hypothesis of equal mean changes between both groups to the average over all post baseline visits will be tested by an appropriate linear contrast of the variable treatment and treatment by visit interaction.. The adjusted mean change from baseline as well as the treatment difference and their corresponding 95% confidence intervals will be presented.

Least square means of each treatment group and estimated treatment differences at visits and corresponding 95% confidence intervals will be tabulated and presented graphically.

2.6.2.2 Proportion of muscle-related adverse events

The null hypothesis to be rejected for the relevant secondary endpoint is:

- H_{03} : The odds regarding participants experiencing at least one muscle-related AE as defined in the SMQ rhabdomyolysis / myopathy from Day 1 to Day 360 are equal between treatment groups.

Muscle-related AEs are defined by the SMQ rhabdomyolysis / myopathy (covering narrow and broad search). The proportion of participants experiencing at least one muscle-related AE from Day 1 to Day 360, i.e. occurring between first dose of double-blind treatment up to the minimum of last contact date and Day 360 visit date, will be analyzed in a logistic regression model. Treatment and CV risk category will be included as factors in the model. The odds ratio and its 95% confidence interval (CI) and p-value will be estimated.

Additionally, the relative risk as well as absolute risk difference and their 95% confidence intervals will be estimated from a Cochran-Mantel-Haenszel test (CMH) stratified for CV risk category.

2.6.2.3 Annualized number of days with pain

Participant reported secondary endpoints are the number of days participants experiencing self-reported pain (at its worst in the last 24 h on a numeric rating scale from 0 (no pain) to 10 (pain as bad as you can imagine)) from Day 1 to Day 360 as reported in the electronic diary. A day with pain is defined as a day with a numeric score > 0. The annualized count (number of days pain) for each participant is calculated as the total counts during the study divided by the total individual observation time of that participant in the double-blind treatment period (between first dose of double-blind treatment up to the minimum of last contact date and Day 360 visit date) where pain diary was completed, multiplied by 365.25.

The null hypothesis to be rejected for the relevant secondary endpoint is:

- H_{04} : The annualized mean number of days pain is experienced is equal between both treatment groups.

The number of pain days experienced will be analyzed using a negative binomial model with the number of observed pain days as the dependent variable and treatment group and CV risk category as fixed-effect factors and the logarithmic follow-up duration (days between first dose of double-blind treatment up to the minimum of last contact date and Day 360 visit date where diary was completed) in years as the off-set. The annualized occurrence rates (i.e. number of pain days per year) and their 95% confidence intervals estimated from the model will be provided by treatment group. The treatment comparison will be performed through the estimated occurrence rates. The occurrence rate ratio and its 95% confidence interval will be provided.

If the negative binomial model fails to converge a quasi-Poisson model will be used instead.

Proportion of patients without any day with pain will be displayed descriptively where pain diary was completed.

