
¹² Lp(a) will only be tested at screening, baseline, Day 90 and EOS. From this sample, triplicate serum aliquots will be made to allow Lp(a) testing in both nmol/L and mg/dL; a third aliquot will be made to allow testing of LDL-C and/or Lp(a) using novel methods currently in development.
 
¹³ A blood draw for PCSK9 levels will also be performed prior to participant switch to PCSK9 mAb, preferably once this switch is granted. The PCSK9 results will remain blinded and will not be used to influence treatment decisions. A plasma aliquot from the PCSK9 blood draw (e.g. SOMA) may also be used to profile proteins related to study drug or dyslipidemia.
 
¹⁴ AST, ALT, ALP, GGT, total bilirubin, CK, creatinine, creatinine clearance, eGFR, chloride, sodium, potassium, fasting glucose, HbA1C. Performed by the central lab.
 
¹⁵ ONLY: AST, ALT, ALP, GGT, CK, Total bilirubin. Performed by the central lab.
 
¹⁶ Hematocrit, Hemoglobin, Red Blood Cell (RBC) Count, Mean Corpuscular Volume (MCV), Mean Corpuscular Hemoglobin (MCH), Mean Corpuscular Hemoglobin Concentration (MCHC), Platelets, Erythrocyte Cell Morphology, White Blood Cell (WBC) count with Differential (Basophils, Eosinophils, Lymphocytes, Monocytes, Neutrophils, Bands). Performed by the central lab.
 
¹⁷ Urinalysis to include: specific gravity, pH, glucose, protein (total), ketones, bilirubin, urobilinogen, nitrite, hemoglobin (blood), leukocytes esterase. If dipstick measurement results are positive (abnormal), microscopic examination will be performed.
 
¹⁸ Done every day during the treatment period, using a digital hand-held device. Participant is to complete the diary everyday at home and the diary will be checked by the investigator at each site visit.
 
¹⁹ Training for each questionnaire should be completed with each participant prior to the first individual participant questionnaire completion.
 
²⁰ The Walking Impairment Questionnaire will only be completed by participants diagnosed with peripheral artery disease (PAD) at Baseline.
 
²¹ The Mac New Heart Disease Health Related Quality of Life Questionnaire will only be completed by participants diagnosed with Angina Pectoris (AP) at Baseline.
 
²² Theoretically, EOT and EOS happen on day 360, but if EOT occurs before the EOS visit, it is recommended that the participant remains in the study until the scheduled EOS. The assessments listed for this visit should only be conducted if the End of Treatment (EOT) and End of Study (EOS) occur simultaneously. An "early Exit" (premature discontinuation from study treatment and study on the same day before day 360) is considered as an EOS visit, and the assessments should be performed as they would be on EOS visit day 360. In case of premature treatment discontinuation, the assessments for the scheduled visit day should be performed (for details refer to Section 8.5.1 and Section 9.1.1).
																			

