12.5.2.2 Muscle-related AE / SMQ rhabdomyolysis / myopathy

The proportion of participants experiencing at least one muscle-related AE as defined in the SMQ rhabdomyolysis / myopathy from day 1 to day 360 will be analyzed in a logistic regression model. Treatment and determined LDL-C target at screening will be included as factors in the model. The LDL-C targets depend on the participants' CV risk category and will be attributed directly from the CV risk category eCRF entries. Therefore, the CV risk category will be included in the model as the stratification factor ("very high risk", "high risk"). The odds ratio and its 95% confidence interval (CI) and p-value will be estimated. The null hypothesis of equal odds will be rejected within the confirmatory testing framework if the 1-sided p-value from the logistic regression model for the factor "treatment" is <0.025 .

Additionally, the relative risk as well as absolute risk difference and their 95% confidence intervals will be estimated from a Cochran-Mantel-Haenszel test (CMH) stratified for the determined LDL-C target before randomization based on the Score statistic.

In case of missing values muscle-related AE / SMQ rhabdomyolysis / myopathy will not be imputed but analyzed according to last known status of the occurrence of an event. To investigate the sensitivity to missing values or potentially different observation times in the two study arms, a time to the first experience of at least one muscle-related AE as defined in the SMQ rhabdomyolysis / myopathy will be conducted.

12.5.2.3 Number of days participants experiencing self-reported pain from day 1 to day 360

The number of pain days experienced will be analyzed using a negative binomial model (P. McCullagh and J.A. 1989) with the number of observed pain days as the dependent variable and treatment group and stratification factor (cardiovascular risk category: very high risk, high risk) as fixed-effect factors and log (follow-up duration in years) as the off-set. The annualized incidence rates and their 95% confidence intervals estimated from the model will be provided by treatment group. The treatment comparison will be performed through the estimated incidence rates. The incidence rate ratio and its 95% confidence interval will be provided.

12.5.2.4 Mean change from baseline in SF-BPI pain severity score and pain interference score at day 360

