2.1.1.3 Treatment arms

The study consists of two treatment arms. Study participants will be assigned to one of the following treatment arms based on randomization in a ratio of 1:1:

- Inclisiran sodium 300 mg s.c.,
- Corresponding placebo.

The investigational treatment duration is planned for 360 days.

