5.5.2.3 Negative binomial model

The third secondary endpoint will be analyzed using a generalized linear model of the following form assuming a negative binomial distribution:

$$\#pain\ days = treatment + CV\ risk\ category + \log(time[y]).$$

In SAS the PROC GENMOD procedure is used with the DIST equal to NB statement to choose the negative binomial distribution and LINK equal to LOG as link function. The offset will be defined in the OFFSET option (eq LOGRISK).

If the model fails to converge a quasi-Poisson model will be fitted instead, with the exception of subgroup analyses.

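### Pain days (H04): the negative binomial model-based standard error is unreliable for a count bounded by diary days, and may be too large or too small

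*SAP*

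**What the plan says.** The daily diary (Protocol Table 8-1, footnote 18) is "Done every day during the treatment period, using a digital hand-held device". SAP 2.6.2.3 turns each entry into a yes/no outcome: "A day with pain is defined as a day with a numeric score > 0". SAP 2.1.1.3 adds: "The investigational treatment duration is planned for 360 days". A participant can therefore have at most about 360 pain days, and never more than the completed diary days that form the offset.

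The model is named in both documents. Protocol 12.5.2.3: "The number of pain days experienced will be analyzed using a negative binomial model". SAP 2.6.2.3: "The number of pain days experienced will be analyzed using a negative binomial model with the number of observed pain days" as the response, with treatment and CV risk category as factors. SAP 5.5.2.3 gives the implementation: "In SAS the PROC GENMOD procedure is used with the DIST equal to NB statement to choose the negative binomial distribution", with a log link and an offset. It names no REPEATED statement or empirical variance.

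The only fallback is in SAP 2.6.2.3, "If the negative binomial model fails to converge a quasi-Poisson model will be used instead", and is repeated in 5.5.2.3. Its trigger is non-convergence, not lack of fit.

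SAP 2.6.2.5 places H04 in the third confirmatory family, with H05 and H06, at one-sided 0.025, and claims strong control of the familywise error rate.

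**The concern.** With the model-based variance, the reported precision is right only if the data follow the assumed mean-variance relation. Here the dispersion k is estimated by maximum likelihood from the whole shape of the distribution, and the variance is then taken as μ + kμ². For a count with a hard ceiling the two need not agree. Many participants at or near zero can push k up, so that the model implies more variance than a bounded count can have. Conversely, a small group in pain every day adds a great deal of real variance while moving the likelihood estimate of k much less.

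The rate ratio itself is not in question; its standard error is. If that is too large, a real reduction in pain days may be missed, and Hommel's procedure loses a small p-value that could have helped H05 and H06. If it is too small, a confirmatory test runs above its stated level. A poor fit of either kind can still converge, so the fallback gives no protection.

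**Working it through.** **Inputs from the documents.** At most one pain day per day over 360 days; negative binomial model with log link and log diary-time offset; one-sided α = 0.025 (SAP 2.6.2.5); about 880 per arm (SAP 3.1).

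**Not in the documents.** No pain-day distribution, expected rate, effect size or power is given for H04, so there is no planned figure to reproduce. SAP 2.1.1.5 confirms that no diary is kept before the first injection, so no pre-treatment data can supply the shape. The shapes below are assumptions: a Beta-distributed daily pain probability, in some cases with added groups of participants who never have pain or have it every day.

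**Formulas.** For a distribution on 0 to 360 with mean μ and SD σ, let k be the value that maximises the expected negative binomial log-likelihood. Per participant, on the log scale:

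- model variance V_M = 1/μ + k
- true variance V_T = σ²/μ²
- ratio r = model SE / true SE = √(V_M / V_T); the sample size cancels
- actual one-sided type I error = Φ(−1.96 r)
- power for an effect that a correct test detects with 80% power = Φ(2.80 − 1.96 r), where 2.80 = 1.96 + 0.84

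**Two worked cases.**

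- Beta(0.5, 2): μ = 72.0, σ = 77.2, k = 1.65. V_M = 0.014 + 1.65 ≈ 1.67; V_T = (77.2/72.0)² = 1.15; r = √(1.67/1.15) = 1.20; power = Φ(0.45) = 67%.
- Beta(1, 20) plus 3% in daily pain: μ = 27.4, σ = 60.8, k = 1.59. V_M = 0.036 + 1.59 = 1.63; V_T = (60.8/27.4)² = 4.92; r = √(1.63/4.92) = 0.58; type I error = Φ(−1.13) = 13%.

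**Results by assumed shape.**

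| Shape | Mean days | r | One-sided type I error | Power (80% if SE correct) |
|---|---|---|---|---|
| 35% never, 20% daily, rest Beta(0.5, 0.5) | 153 | 2.22 | <0.1% | 6% |
| Beta(0.5, 0.5) | 180 | 1.49 | 0.2% | 45% |
| Beta(0.35, 0.65) | 126 | 1.45 | 0.2% | 48% |
| 20% never, 10% daily, rest Beta(0.5, 2) | 86 | 1.41 | 0.3% | 51% |
| Beta(0.5, 2) | 72 | 1.20 | 0.9% | 67% |
| Beta(1, 10) | 33 | 1.05 | 2.0% | 77% |
| Beta(0.5, 20) + 10% daily | 44 | 0.83 | 5.2% | not meaningful |
| Beta(1, 10) + 5% daily | 49 | 0.75 | 7.2% | not meaningful |
| Beta(1, 20) + 3% daily | 27 | 0.58 | 13.0% | not meaningful |

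For Beta(0.35, 0.65) and Beta(0.5, 0.5) the fitted model puts 9% and 14% of its probability above 360 days, where no observation can lie.

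**Check by simulation** (880 per arm, varying diary days, treatment and CV risk in the model, log offset; 250 to 500 trials per scenario). In the last three shapes, in table order, simulated type I error with the model SE was 6.2%, 5.8% and 14.2%. With the sandwich SE it was 3.2%, 1.6% and 2.8%. Across all null scenarios the sandwich SE gave 1.6% to 3.7%, consistent with 2.5% given a Monte Carlo error of about 0.7 points.

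Simulated power, model SE against sandwich SE:

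- Beta(0.3, 0.3), rate ratio 0.90: 31% against 80%
- 20% never, 10% daily, rest Beta(0.5, 2), rate ratio 0.84: 48% against 80%
- Beta(0.5, 2), rate ratio 0.866: 67% against 80%
- Beta(1, 10), rate ratio 0.87: 87% against 88%

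**The case against.** The strongest reply is that nothing here shows the plan will fail. Every ratio comes from an assumed distribution, and for low, unimodal counts the planned analysis is nearly correct. Where the standard error is too large, the test is conservative and yields no false claim. H04 is reached only if H01, H02 and H03 are all rejected, and the visible sample-size text does not power the trial for it. SAP 2.6.6.2 to 2.6.6.4 are blacked out and might hold a supporting pain-day analysis.

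Most of this stands, and it limits the point. A reader might infer that the negative binomial model always gives too wide an interval here, by some fixed percentage, and so throws away most of the power. The documents do not support that: they say nothing about how pain days are distributed, and equally admissible shapes give an interval that is too narrow. A reader might also infer that the quasi-Poisson fallback can never be reached; it can only be said that poor fit need not trigger it.

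What does not stand is the conclusion that nothing need be done. The reassurance about conservatism covers one direction only. A redacted supplementary analysis would not alter the variance behind the confirmatory p-value. The place of H04 in the hierarchy limits how often the problem matters, but not the validity of the test once it is reached.

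**Conclusion.** The model-based standard error specified for H04 cannot be relied on for a count capped by diary days. Its error is unknown in size and direction before the data are seen. Over the assumed shapes r runs from about 0.6 to 2.2. Between r = 1.2 and r = 1.5, 80% power falls to about 67% to 45%; with mostly low counts and a small daily-pain group, one-sided type I error is about 5% to 13% instead of 2.5%. The second possibility is the more serious, because it would undermine the strong familywise error control claimed in SAP 2.6.2.5.

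That the count is bounded and that no robust variance is named follow from the text. The magnitudes rest on assumed distributions. The large-sample ratios also take 360 diary days for everyone, and the Hommel adjustment within the third family was not modelled.

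**What to change.** Keep the log-link rate model, its factors, the diary-time offset and the rate ratio. Base the H04 confidence interval and one-sided p-value on the empirical (sandwich) variance by adding a REPEATED statement with SUBJECT= the participant identifier in PROC GENMOD. Report the model-based negative binomial result as a sensitivity analysis. Because Protocol 12.5.2.3 names the negative binomial model, record the change in SAP section 4, and do so before unblinding; choosing a variance estimator afterwards would look data-driven.

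Possible wording: H04 will be tested with the log-link negative binomial rate model, using the empirical sandwich variance for the confidence interval and one-sided p-value; model-based results will be presented as a sensitivity analysis.

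Making quasi-Poisson the main analysis would also work (simulated type I error 2.0% to 3.5%), but it departs further from the protocol-named model.

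The cost is a short SAP entry and one line of code, with no new data. The downside is a small departure from the protocol-named analysis and, where r is below 1, a wider interval: 1/0.83 = 1.2 to 1/0.58 = 1.7 times as wide in the cases above, which is the width the data warrant.
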